8.3 REPORTING OF SERIOUS ADVERSE EVENTS

Any AE that meets protocol-defined serious criteria that require expedited reporting must be submitted immediately (within 24 hours of awareness) to OSRO Safety using the CCR SAE report form.

All SAE reporting must include the elements described in section [8.2](#).

SAE reports will be submitted to the Center for Cancer Research (CCR) at:

[contact] and to the CCR PI and study coordinator. CCR SAE report form and instructions can be found at:

<https://ccrod.cancer.gov/confluence/display/CCRCRO/Forms+and+Instructions>

Following the assessment of the SAE by OSRO, other supporting documentation of the event may be requested by the OSRO Safety and should be provided as soon as possible.

8.4 WAIVER OF EXPEDITED REPORTING TO CCR

Death or hospitalization that is deemed to be due to disease progression, and not attributable to the intervention will not be reported as an SAE. The event, and the assessment that it was caused by disease progression will be documented in the medical records. The causality assessment of Hospitalization will be re-evaluated any time when new information is received. If the causality assessment changes from disease progression to related to the study intervention, SAE report will be sent to the Sponsor immediately in an expedited manner according to section [8.3](#). If there is any uncertainty whether the intervention is a contributing factor to the event, the event should be reported as AE or SAE as appropriate.

8.5 REPORTING PREGNANCY

All required pregnancy reports/follow-up to OSRO will be submitted to:

[contact] and to the CCR PI and study coordinator.

Forms and instructions can be found here:

<https://ccrod.cancer.gov/confluence/display/CCRCRO/Forms+and+Instructions>

8.5.1 Maternal Exposure

If a participant becomes pregnant while actively on study intervention, the study intervention should be discontinued immediately, and the pregnancy reported to the Sponsor no later than 24 hours of when the Investigator becomes aware of it. The Investigator should notify the Sponsor no later than 24 hours of when the outcome of the Pregnancy becomes known.

Pregnancy itself is not regarded as an SAE. However, congenital abnormalities or birth defects and spontaneous miscarriages that meet serious criteria (section [8.1.2](#)) should be reported as SAEs.

The outcome of all pregnancies should be followed up and documented.

8.5.2 Paternal Exposure

Male participants should refrain from fathering a child or donating sperm during the study and for 2 months after the last dose of ¹⁸F-DCFPyL.

Pregnancy of the participant's partner is not considered to be an AE. The outcome of all pregnancies occurring from the date of the first dose until 2 months after the last imaging should,

if possible, be followed up and documented. Pregnant partners may be offered the opportunity to participate in an institutional pregnancy registry protocol (e.g., the NIH IRP pregnancy registry study) to provide data about the outcome of the pregnancy for safety reporting purposes.

8.6 REGULATORY REPORTING FOR STUDIES CONDUCTED UNDER CCR SPONSORED IND

Following notification from the investigator, CCR, the IND sponsor, will report any suspected adverse reaction that is both serious and unexpected. CCR will report an AE as a suspected adverse reaction only if there is evidence to suggest a causal relationship between the study product and the adverse event. CCR will notify FDA and all participating investigators (i.e., all investigators to whom the sponsor is providing drug under its INDs or under any investigator's IND) in an IND safety report of potential serious risks from clinical trials or any other source, as soon as possible, in accordance to 21 CFR Part 312.32.

All serious events will be reported to the FDA at least annually in a summary format.

8.7 SPONSOR PROTOCOL DEVIATION REPORTING

A Protocol Deviation is defined as any non-compliance with the clinical trial Protocol, Manual of Operational Procedures (MOP) and other Sponsor approved study related documents, GCP, or protocol-specific procedural requirements on the part of the participant, the Investigator, or the study site staff inclusive of site personnel performing procedures or providing services in support of the clinical trial.

It is the responsibility of the study Staff to document any protocol deviation identified by the Staff or the site Monitor in the CCR Protocol Deviation Tracking System (PDTs) online application. The entries into the PDTs online application should be timely, complete, and maintained per CCR PDTs user requirements.

In addition, any deviation to the protocol should be documented in the participant's source records and reported to the reviewing IRB per their guidelines. OSRO required protocol deviation reporting is consistent with E6(R2) GCP: Integrated Addendum to ICH E6(R1): 4.5 Compliance with Protocol; 5.18.3 (a), and 5.20 Noncompliance; and ICH E3 16.2.2 Protocol deviations.

9 CLINICAL MONITORING PLAN

Clinical site monitoring is conducted to ensure:

- that the rights of the participants are protected;
- that the study is implemented per the approved protocol, Good Clinical Practice and standard operating procedures; and,
- the quality and integrity of study data and data collection methods are maintained.

Monitoring for this study will be performed by NCI CCR Office of Sponsor and Regulatory Oversight (OSRO) and Regulatory Oversight Support (SROS) Services contractor. Clinical site monitoring activities will be based on OSRO standards, FDA Guidance E6(R2) Good Clinical Practice: Integrated Addendum to ICH E6(R1) March 2018, and applicable regulatory requirements.

Details of clinical site monitoring will be documented in a Clinical Monitoring Plan (CMP) developed by OSRO. CMPs will be protocol-specific, risk-based and tailored to address human subject protections and integrity of the study data. OSRO will determine the intensity and frequency of monitoring based on several factors, including study type, phase, risk, complexity, expected enrollment rate, and any unique attributes of the study and the site. The Sponsor will conduct a periodic review of the CMP to confirm the plan's continued appropriateness. A change to the protocol, significant or pervasive non-compliance with GCP, or the protocol may trigger CMP updates.

OSRO SROS Monitoring visits and related activities will be conducted throughout the life cycle of each protocol. The first activity is before the study starts to conduct a Site Assessment Visit (SAV) (as warranted), followed by a Site Initiation Visit (SIV), Interim Monitoring Visit(s) (IMVs), and a study Close-Out Visit (COV).

Some monitoring activities may be performed remotely, while others will occur at the study site(s). Monitoring visit reports will describe visit activities, observations, and associated action items or follow-up required for resolution of any issues, discrepancies, or deviations. Monitoring reports will be distributed to the study PI, NCI CCR QA, CCR Protocol Support Office, coordinating center (if applicable), and the Sponsor regulatory file.

The site Monitor will inform the study team of any deviations observed during monitoring visits. If unresolved, the Monitor will request that the site Staff enter the deviations in the CCR Protocol Deviation Tracking System (PDTs) for deviation reporting to the Sponsor and as applicable per institutional and IRB guidance.

10 STATISTICAL CONSIDERATIONS

10.1 PRIMARY ENDPOINT

¹⁸F-DCFPyL PET/CT will be used to identify positive suspected sites, which will be correlated with histopathology results. For lesions within the liver, a focal abnormal area of increased ¹⁸F-DCFPyL activity higher than the surrounding liver uptake (SUV_{max} more than x 1.2 times than the normal liver-SUV mean) will be considered positive. For lesions outside the liver, a positive lesion is defined as focal abnormal uptake higher than the blood pool, or the surrounding normal organ or soft tissue background. Pathological anatomic imaging but lacking DCFPyL uptake would indicate a type of tumor that fails to express PSMA. The performance of ¹⁸F-DCFPyL PET/CT is assessed by the positive predictive value which is defined as the proportion of histopathology positive lesions.

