1.3.3 Hepatocellular Carcinoma and PSMA

It has been shown that PSMA can be expressed not only on prostate cancer cells, but also on cell lines of other malignancies, as well as tumor endothelium. A recent publication reported that nearly 95% of hepatocellular cancers stained positive for PSMA in the tumor vasculature. Zhu et al. [22] suggested that the process of endothelial cell recruitment to HCC occurs early and throughout the process of hepatic tumorigenesis, making an endothelial cell tracer an ideal marker to detect early disease. In a recent study assessing 100 HCC tissue samples using immunohistochemical staining, Jiao and collaborators [23] reported PSMA expression in more than 50% of tumor-associated vasculature in 26% of tissues, and PSMA expression in less than 50% of vasculature in 48% of tissues. Furthermore, high vascular PSMA expression was also associated with poor prognosis in participants with HCC, and could be used as an independent prognostic marker for HCC [23]. Tolkach et al. [24] found that the majority of hepatocellular carcinomas (89.9%) show high levels of PSMA expression on tumor neovasculature and on canalicular membrane of the tumor cells (4.1% of tumors) [24]. To date, most of the reported findings with PSMA-targeted PET radiotracers in HCC have been in few case reports [25] and small case series [26]. Recently, ⁶⁸Ga-PSMA PET imaging showed encouraging preliminary results for imaging HCC in a small cohort of 7 participants. ⁶⁸Ga-PSMA PET-CT showed superiority over ¹⁸F-FDG PET-CT in imaging participants with HCC. All but a single tumor lesion were associated with ⁶⁸Ga-PSMA uptake higher than that of the surrounding liver

parenchyma (**Figure 2** and **Figure 3**), with a mean uptake 3.6 times higher than that of the background liver. The increased ⁶⁸Ga-PSMA uptake in HCC was corroborated by the results of immunohistochemistry analysis showing PSMA staining of the endothelial cells lining of vessels that are penetrated by tumor. Furthermore, ⁶⁸Ga-PSMA PET appeared to differentiate necrotic from viable tumor (**Figure 3**), which could dramatically improve detection of HCC recurrence following local ablative therapies [26]. In another recent study, Kuyumcu et al. [27] was able to visualize advanced HCC using ⁶⁸Ga-PSMA-PET/CT in 16 out of 19 cases with high tumor-to-background ratio. Interestingly, ⁶⁸Ga-PSMA standard uptake value (SUV_{max}) correlated with participant overall survival [27].

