3 STUDY IMPLEMENTATION

3.1 STUDY DESIGN

This is an open-label multi-center study recruiting participants with suspected hepatocellular carcinoma (with at least one detectable liver lesion on standard of care CT and/or MRI) who are eligible to undergo local treatment for HCC (e.g., surgical resection, radiofrequency ablation, microwave ablation, transarterial embolization (TAE), stereotactic body radiotherapy (SBRT)). Participants will be consented and enrolled through the NIH Clinical Center.

All participants will undergo a baseline ¹⁸F-DCFPyL PET/CT. Within approximately 2 weeks of each ¹⁸F-DCFPyL PET/CT scan, participants will also be scanned with a ¹⁸F-FDG PET/CT imaging. ¹⁸F-FDG PET/CT may be performed within two weeks before or after each ¹⁸F-DCFPyL PET/CT scan. Each PET/CT imaging must be approximately a day apart. The order obtained for ¹⁸F-DCFPyL PET/CT and ¹⁸F-FDG PET/CT does not matter.

A CT and/or MRI will be performed within 2 months of the ¹⁸F-DCFPyL PET/CT scan. Clinical scans performed in this time frame by local providers are also acceptable.

Participants will undergo a biopsy prior to/concurrent with local therapy (more than one lesion may be biopsied during the same procedure). The procedure may be performed at the NIH Clinical Center or at the participating site (Washington DC Veteran's Affairs Medical Center). The treatment procedure will be scheduled as clinically indicated and samples will be collected prior to therapy (or during surgical resection).

An additional ¹⁸F-DCFPyL PET/CT imaging will be performed during the first routine post local therapy follow-up for participants with a positive baseline ¹⁸F-DCFPyL-PET/CT (i.e. the presence of DCFPyL-avid tumor/s) and with a biopsy confirming HCC diagnosis. Subjects with negative tumor uptake at the baseline ¹⁸F-DCFPyL-PET/CT and with a biopsy confirming HCC, will not have study-related imaging post-treatment and will remain in follow-up. Subjects with biopsies negative for HCC will be taken off protocol.

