6.3.1.1 Image Analysis

Target Lesions: Images will be analyzed by MIB staff by identifying, recording and measuring measurable target lesions. A segmentation tool will be applied to generate semi-automated volume of interests (VOI) within the target lesion(s). Maximum standardized uptake value (SUV_{max}) and tumor volumes will be extracted from the generated target lesion(s) VOIs. ^{18}F -DCFPyL uptake in major organs and bone marrow will also be measured and mean SUV values will be extracted.

All other lesions (or sites of disease) including any measurable lesions should be identified as non-target lesions and should also be recorded.

Antitumor effect: To determine whether uptake of ^{18}F -DCFPyL correlates with response to therapy, target tumor(s) imaging PET parameters, including SUV_{max} , and tumor volume will be compared between responders vs non-responders. Participant response will be based on RECIST 1.1. criteria and clinical assessment.

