10.4 SAMPLE SIZE DETERMINATION

Sample size was calculated such that the limits of the 95% expected confidence interval to the true lesion level positive predicted value is less than 15%. The lesion level positive predictive value is the proportion of biopsy positive lesions. Assume 80% of the participants enrolled to the study each have 1-2 lesions identified by ^{18}F -DCFPyL PET/CT with 0.2 modest inter-lesion correlation, and the positive predictive value is 70%. A sample size of 40 evaluable participants accrued to the study produces a two-sided 95% confidence interval with the distance from the positive predictive value to the limits equal to 0.148. An evaluable participant is defined as a participant who completes all required study procedures. To account for inevaluable participants, the accrual ceiling will be set to 50.

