10.6 ANALYSIS OF THE SECONDARY ENDPOINTS

- The lesion level sensitivity, specificity and positive predictive value of ^{18}F -DCFPyL PET/CT and CT/MRI will be calculated and compared. The confidence interval for each estimate will be obtained from the bootstrap samples as described in **10.5** and the difference in the estimates between the imaging modalities will be compared by the Wald test with the standard error calculated from the bootstrap samples.
- For ^{18}F -DCFPyL PET/CT positive participants who undergo local treatment for HCC, change in ^{18}F -DCFPyL PET/CT uptake between pre- and post-treatment of tumor or tumor bed will be compared by paired Wilcoxon test.

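### Every 18F-DCFPyL accuracy result for liver lesions rests on one unreferenced 1.2x cut, and no planned analysis relates the continuous uptake ratio to histology

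*Combined protocol and SAP*

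**What the plan says.** All references are to the Combined protocol and SAP.

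- **Positivity (10.1).** A liver lesion is positive if its SUVmax is "more than x 1.2 times than the normal liver-SUV mean) will be considered positive". No reference or reason for 1.2 is given. Lesions outside the liver are judged against background, with no numeric rule.
- **Primary measure (10.1, 10.5).** Performance is "assessed by the positive predictive value which is defined as the proportion of histopathology positive lesions", reported with a bootstrap interval. The 2000 bootstrap samples are to be drawn at participant level without replacement.
- **Secondary accuracy (10.2, 10.6).** "The lesion level sensitivity, specificity and positive predictive value of" DCFPyL PET/CT and CT/MRI will be compared by a Wald test. That test is between modalities, not between HCC and non-HCC lesions.
- **Sizing (10.4).** The target is a distance from the "limits of the 95% expected confidence interval to the true lesion level positive predicted value is less than 15" percent. No null value or power is stated.
- **Continuous uptake (6.3.1.1, 10.6, 10.7).** SUVmax and "tumor volumes will be extracted from the generated target lesion(s) VOIs", and mean SUV is taken for major organs. Uptake is then related to treatment change and response, CT/MRI grade, PSMA staining, FDG uptake and survival. Section 5.2.1 says specimen results, which include the tumour diagnosis, will be correlated with the PET/CT results, but gives no method.
- **Histology (3.1).** "Participants will undergo a biopsy prior to/concurrent with local therapy". This applies whether or not the baseline DCFPyL scan is positive, and participants without HCC leave the study only after biopsy.

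**The concern.** The primary objective is to assess how well the scan detects HCC. The quantity measured is a ratio on a continuous scale, but the accuracy results keep only which side of 1.2 it falls on. Nothing in the documents shows where 1.2 lies in the distribution of ratios for HCC and non-HCC lesions.

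If the PPV comes out mediocre, there are two explanations with different consequences. Either uptake does not separate HCC from other lesions, or it does and 1.2 is a poor place to divide them. Sensitivity and specificity at the same cut cannot settle this, because they describe the same single point on the curve. Section 1.3.4 says the study should support a future trial and help define the tracer's role, and for that the distinction matters.

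**Working it through.** **1. The plan's own figure.** Inputs from 10.4: 40 evaluable participants, "Assume 80% of the participants enrolled to the study each have 1-2 lesions identified by" the scan, PPV p = 0.70, inter-lesion correlation 0.2. That gives 40 × 0.8 = 32 participants with PET-identified lesions. The mix of one and two lesions is not stated.

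Half-width = 1.96 × sqrt(p(1−p) × Σ mᵢ[1 + (mᵢ−1) × 0.2]) / Σ mᵢ

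If 8 of the 32 have two lesions: Σ mᵢ = 40, the weighted sum is 24 + 8 × 2 × 1.2 = 43.2, and the half-width is 1.96 × sqrt(0.21 × 43.2)/40 = 0.1476. This rounds to the stated 0.148. All single lesions gives 0.159, and all double gives 0.123. Nothing below changes this figure.

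**2. What the planning values imply if read per lesion (assumption).** With 80% of lesions positive and PPV 0.70, HCC-and-positive is 0.8 × 0.7 = 0.56 of lesions, and non-HCC-and-positive is 0.8 × 0.3 = 0.24. For HCC prevalence π, sensitivity = 0.56/π and false-positive rate = 0.24/(1−π). Prevalence must be at least 0.56. The scan is informative only if the PPV exceeds π, so π must be below 0.70. The documents do not state π.

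**3. Separation behind the same PPV.** Assume an equal-variance binormal log-ratio: d = z(sensitivity) − z(false-positive rate), AUC = Φ(d/√2).

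| π | Sensitivity | False-positive rate | d | AUC |
|---|---|---|---|---|
| 0.60 | 0.933 | 0.600 | 1.25 | 0.81 |
| 0.62 | 0.903 | 0.632 | 0.96 | 0.75 |
| 0.64 | 0.875 | 0.667 | 0.72 | 0.70 |
| 0.66 | 0.848 | 0.706 | 0.49 | 0.64 |
| 0.68 | 0.824 | 0.750 | 0.25 | 0.57 |

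All five rows have PPV 0.70. At π = 0.60, moving the cut midway between the two means gives sensitivity Φ(0.624) = 0.734 and false-positive rate 0.266. PPV is then 0.6 × 0.734 / (0.6 × 0.734 + 0.4 × 0.266) = 0.81. The same move at π = 0.66 (sensitivity Φ(0.2445) = 0.597) gives 0.66 × 0.597 / (0.66 × 0.597 + 0.34 × 0.403) = 0.74. A PPV of 0.70 therefore fits both a good tracer with a poor cut and a weak tracer.

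**4. Illustrative power.** 40 independent lesions, two-sided 5%, 2,500 simulated trials per cell; a repeat with 6,000 agreed to within 2 points. At AUC 0.57 no test has useful power, and the gap over chi-square is only 1 to 2 points.

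| AUC | Fisher | Chi-square | Mann-Whitney on ratio | Gap: chi-square / Fisher |
|---|---|---|---|---|
| 0.81 | 68% | 75% | 95% | 20 / 27 |
| 0.75 | 48% | 56% | 78% | 22 / 30 |
| 0.70 | 29% | 37% | 53% | 16 / 24 |
| 0.64 | 15% | 21% | 27% | 6 / 12 |

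**5. A higher HCC share.** Eligibility is LR4 or LR5 (2.1.1), so 85 to 90% HCC is plausible. It cannot coexist with step 2, where π can be at most 1 − 0.24 = 0.76. So PPV is left free and the cut is placed at an assumed sensitivity of 0.84, from 16/19 cases seen with a related tracer (1.3.3). With 40 lesions and AUC 0.70 to 0.80 (6,000 trials per cell), the gap over chi-square is about 2 to 6 points at 85% HCC and about −3 to 0 at 90%. Over Fisher it is 12 to 18 and 9 to 15 points. Only about 6 (40 × 0.15) or 4 (40 × 0.10) lesions are then non-HCC, so chi-square is only approximate.

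**6. Precision of an added AUC (Hanley-McNeil).** Let n₁ be the HCC lesions, n₀ the non-HCC lesions and A = 0.75. Then A/(2−A) = 0.600, 2A²/(1+A) = 0.643 and A² = 0.5625. Variance = [0.1875 + (n₁−1) × 0.0375 + (n₀−1) × 0.0804]/(n₁n₀). For an assumed 48 lesions treated as independent, 34 HCC and 14 non-HCC give a half-width of 0.14; 41 and 7 give 0.17.

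**The case against.** The strongest objection is that the trial is sized for the width of a PPV interval. PPV needs a binary call, and a fixed, prespecified cut is legitimate because it avoids the optimism of choosing a cut from the data. This stands, and it is why 1.2 should remain the primary rule.

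Four stronger readings are tempting, and the documents do not support them.

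- *The trial loses 10 to 30 points of power whenever separation is moderate.* No test of HCC against non-HCC is planned, so no planned power is lost. The size of the gap depends on the HCC share, the position of the cut and the test, none of which the documents fix. Step 5 shows it vanishing against chi-square.
- *Every accuracy result depends on 1.2.* CT/MRI and FDG accuracy do not use it, and neither do lesions outside the liver.
- *The background contradicts 1.2.* Section 1.3.3 reports HCC "with a mean uptake 3.6 times higher than that of the background liver", but this is a mean, for 68Ga-PSMA, in 7 participants. It is compatible with a positivity floor of 1.2.
- *All the data are already secured.* The 1.2 rule needs both parts of the ratio, but 6.3.1.1 extracts SUVmax only from target-lesion volumes. It does not say how a volume is drawn on a non-avid lesion.

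Section 5.2.1 does promise a correlation with specimen results. Without a stated method or contrast, it does not fill the gap.

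**Conclusion.** The point holds as a gap in the analysis plan, not as an error in the sample size. For liver lesions, PPV, sensitivity and specificity of DCFPyL all rest on one unreferenced cut. No specified analysis of the continuous ratio against histology would show whether a disappointing result belongs to the tracer or to the cut. PPV precision is unchanged.

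The power gaps in step 4 illustrate how much information the cut can discard. They assume independent lesions, a binormal ratio, and planning values given for participants but read per lesion. They should not be quoted as a loss suffered by this trial. The change is a cheap improvement, and making it before the data are examined keeps the analysis prespecified.

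**What to change.** Keep the 1.2 rule and PPV as primary, and state the basis for 1.2 in 10.1. Add a supportive analysis to 10.2 and 10.6 (or 10.3 and 10.7), for example:

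> For all biopsied liver lesions, PET-positive and PET-negative, lesion SUVmax and normal-liver SUVmean will be recorded. The area under the ROC curve of their ratio against histology (HCC or not HCC) will be estimated, with a 95% percentile interval from 2000 bootstrap samples of participants drawn with replacement. Any cut read from the curve is hypothesis-generating and does not replace 1.2.

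Two consequential edits are needed. Section 10.5 should also say with replacement: drawing all participants without replacement returns the same data each time and gives an interval of zero width. Section 6.3.1.1 should say how SUVmax is measured on biopsied lesions that are non-target or show no uptake.

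The cost is a few sentences, one extra analysis and some added measurements. The result covers biopsied liver lesions only. Its interval will be wide: a half-width of about 0.14 to 0.17 at AUC 0.75 with 48 lesions, and wider with fewer non-HCC lesions. Presenting it as an estimate without a formal test avoids ranking it against the existing secondary comparisons.
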